4.5.3 Rescue Medications or Treatments

Allergan provided artificial tears (SAT, see Study Procedures Manual) may be used during the study (from the vehicle run-in (day -14) visit until the month 6 visit) only as needed as rescue medication for intolerable symptoms. In order to avoid dilution of the study medication, SAT should be instilled at least 30 minutes before or 30 minutes after each use of the study treatment.

Patients will be asked to refrain from use of SAT for 1 day prior to each study visit. "One day prior to each study visit" is defined as the morning of the day before the study visit and continues until the end of the study visit.

At each visit, patients will be asked about their use of artificial tears (SAT) by responding to the following 2 questions: 1) number of times used during the day prior to the study visit, and 2) how many times used per day on average over the week prior to the study visit.

5. Study Treatments

5.1 Study Treatments and Formulations

0.1% [REDACTED] (AGN-195263) (10192X) [REDACTED]

[REDACTED]

[REDACTED]

[REDACTED]

[REDACTED]

5.2 Control Treatment

The control treatment in this study is a vehicle of 0.1% [REDACTED] (AGN-195263) [REDACTED]. The vehicle contains the same inactive ingredients as that of the 0.1% AGN-195263, but does not contain the drug substance.

5.3 Methods for Masking

During the vehicle run-in period (days -14 to -1), the patient will be masked to the run-in study treatment he/she receives. In order to maintain the masking of study vehicle during the vehicle run-in period (and to obtain unbiased ocular symptoms), patients will be informed and consented that they will receive vehicle for a 2-week period during their study participation. Following the vehicle run-in period, the investigator and patient will be masked during the randomized study treatment phase (baseline (day 1) to month 6 visit). All study treatments will be provided in identical unit dose vials and cartons to maintain masking of the study. From the end of the month 6 visit until the month 12/study exit visit (the open-label treatment extension phase), the investigator and patient will be unmasked.

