Vehicle Run-in Visit (day -14): All patients will enter a 2-week, patient-masked run-in on vehicle, where 1 drop of 0.1% AGN-195263 vehicle will be administered twice daily (morning and evening, spaced approximately by 12 hours) in each eye.

Baseline Visit (Randomization to Study Treatment and Initiation of Twice Daily Dosing [day 1]): Patients will be randomized on day 1 to receive either 0.1% AGN-195263 or its vehicle, administered as a single drop, twice daily (morning and evening, spaced approximately by 12 hours) in each eye. Both patient and investigator will be masked.

Month 1 Visit: Office visit during the randomized study treatment period. For selected patients, blood sample collection for systemic pharmacokinetics will occur (at same time \pm 1 hour of pre-dose blood sample collection at the standardization (day -21) visit) prior to in-office administration of study treatment and for 12 hours after administration of study treatment at the following intervals: 5 ± 1 min; 10 ± 1 min; 30 ± 5 min; 2 hrs \pm 15 min; 4 hrs \pm 30 min; 6 hrs \pm 30 min; 12 hrs \pm 30 min. Following the 12 hour sample collection, site staff will remind patient to administer 1 drop of study treatment in each eye prior to leaving site.

Month 3 Visit: Office visit during the randomized study treatment period. For selected patients, a single blood sample collection for systemic pharmacokinetics will occur (at same time \pm 1 hour of pre-dose blood sample collection at the standardization (day -21) visit) prior to in-office administration of study treatment.

Month 6 Visit: Primary and secondary efficacy will be assessed at the month 6 visit, after which the open-label treatment extension period starts. All patients will receive 0.1% AGN-195263, administered as a single drop, twice daily (morning and evening, spaced approximately by 12 hours) in each eye. Both patient and investigator will be unmasked. For select patients, blood sample collection for systemic pharmacokinetics will occur (at same time \pm 1 hour of pre-dose blood sample collection at the standardization (day -21) visit) prior to in-office administration of study treatment and 10 ± 1 min after administration of study treatment.

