6.5 Summary of Methods of Data Collection

This protocol will use electronic case report forms (eCRFs) with remote data capture through a qualified third-party vendor. Data entered into the eCRF will correspond to, and be supported by, source documentation maintained at the sites. The investigator is responsible for ensuring that data are properly recorded on each patient's eCRFs and related documents. The data will be entered on the eCRFs in a timely manner and on an ongoing basis. Site data and images will be transferred to Allergan via electronic media.

An IxRS will be used to assign patient identification numbers, randomize patients, and manage study medication inventory. Data will be transferred to Allergan on a periodic basis throughout the study.

7. Statistical Procedures

The primary efficacy analysis will be performed after all patients complete the month 6 visit or discontinue from the study prior to the month 6 visit. The final analysis will be performed after all patients exit the study. There will be separate database locks for the primary analysis and final analysis. Prior to the first database lock a detailed analysis plan (AP) will be approved.

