7.1 Analysis Populations

There are 3 analysis populations defined for this study: intent-to-treat (ITT), per-protocol (PP), and safety.

The ITT population comprises all randomized patients. The efficacy variables will be analyzed using the ITT population. The analyses will be performed per the randomization schedule.

The PP population comprises all randomized and treated patients who met the key inclusion and exclusion criteria; did not use artificial tears (including SAT), lid hygiene, or other prohibited treatments that could impact the overall ocular discomfort score at month 6; and had no other major protocol deviations. The PP population will be determined prior to database lock. The primary efficacy variable will be analyzed using the PP population on an as-treated basis.

The safety population is defined as all patients who received at least 1 dose of study medication. Safety analyses will be performed on an as-treated basis. All safety measures will be analyzed using the safety population.

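### As written, patient and investigator are unmasked at each patient's month 6 visit, which permits sites to learn the randomised arm before the primary lock

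*Combined protocol and SAP*

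**What the plan says.** Section 5.3 masks investigator and patient from baseline to the month 6 visit. "From the end of the month 6 visit until the month 12/study exit visit", which it identifies as the open-label extension phase, "the investigator and patient will be unmasked". The month 6 entry in Section 3.1 first says that all patients will then receive the active drug, and adds: "Both patient and investigator will be unmasked".

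The opening of Section 7 sets the timing of the analysis: "The primary efficacy analysis will be performed after all patients complete the month 6 visit" or have left before it. It adds that "There will be separate database locks for the primary analysis and final analysis".

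On the per-protocol set, Section 7.1 says: "The PP population will be determined prior to database lock". It does not say which of the two locks is meant, who decides, or whether they are masked.

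Section 7.3 makes a patient a non-responder at month 6, whatever the score, after any of the following:
- artificial tear use, including SAT, within 24 hours before the visit
- lid hygiene on at least 8 of the preceding 30 days, or at all within 14 days
- any post-randomisation use of the listed macrolide or tetracycline antibiotics

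Section 7.3.1 applies this override in the primary ITT analysis.

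**The concern.** Unmasking is tied to each patient's own visit; the lock is tied to the last patient's visit. Between the two, month 6 records can still be queried and corrected by the site. If the site knows the arm in that interval, later decisions about those records are no longer masked.

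Two kinds of site-entered data matter:
- **Concomitant use.** The artificial tear, lid hygiene and antibiotic entries decide whether a score of 0 counts as a response. Because the override works inside the ITT analysis, using the ITT population does not protect against arm-aware correction of these entries.
- **Adverse event causality.** Section 9.1.4 makes this a judgement, and Section 7.3.4 uses it for the treatment-related tables. It does not enter the primary endpoint.

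The documents give no purpose for disclosing the randomised arm at this point. Everyone receives the same drug after month 6, and Section 9.4 already covers unmasking for a patient's safety.

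**Working it through.** The point concerns masking and timing, so the main check is a comparison of sections. Arithmetic is needed only for the number of patients affected and for one illustration.

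**1. The plan's own figure.** Section 7.6 gives rates of 20.0% and 9.8%, two-sided alpha 0.05, 85% power, and a pooled z-test with continuity correction.
- Mean rate = (0.200 + 0.098)/2 = 0.149; difference d = 0.102.
- Uncorrected n = [1.960 × √(2 × 0.149 × 0.851) + 1.036 × √(0.200 × 0.800 + 0.098 × 0.902)]² / 0.102² = 217.3, so 218 per group.
- Corrected n = (217.3/4) × [1 + √(1 + 4/(217.3 × 0.102))]² = 236.5, so 237 per group.
- Total = 2 × 237 = 474; 474/0.90 = 526.7, so 527.

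The stated 237 and 527 are reproduced, and this point does not change them.

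**2. Patients affected.** Taking the 10% attrition as loss before month 6, planned completers are 527 × 0.90 = 474.3, about 474. The other 53 or so leave before month 6 and are not covered by this unmasking. All completers except those whose month 6 visit comes last would enter the unmasked phase with the primary database still open. The earliest would do so by up to about the length of recruitment, which is not stated.

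**3. What is fixed before unmasking, and what is not.**

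| Item | Collected | Can be corrected after unmasking? |
|---|---|---|
| Month 6 discomfort score | During the visit, masked (3.1) | Only through a correction to the record |
| Artificial tear, lid hygiene and antibiotic use | Asked at the visit, masked (4.5.3, 8.3.7) | Yes; site-entered history, and the same topics are asked again at month 9 (8.3.8) |
| Adverse event causality | Throughout (9.1.4) | Yes |
| PP membership | Before an unspecified lock (7.1) | Decider and masking not stated |

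**4. Who is unmasked.** Sections 3.1 and 5.3 name only patient and investigator. Section 7.5 lets randomisation codes be released so that only active-arm PK samples are assayed, under internal procedures that are not described. No section says that data managers, statisticians or PP reviewers are unmasked, and none says that they stay masked.

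**5. Illustration only.** Suppose both true rates are 9.8%, and arm-aware corrections move the rates apart by s. With 237 per group and an uncorrected two-sided z-test, take s = 0.02:
- SE under the null = √(0.108 × 0.892 × 2/237) = 0.0285; the critical difference is 1.960 × 0.0285 = 0.0559.
- SE under the shift = √[(0.118 × 0.882 + 0.098 × 0.902)/237] = 0.0285.
- Rejection probability = P(Z > (0.0559 − 0.02)/0.0285) + P(Z < (−0.0559 − 0.02)/0.0285) = 0.104 + 0.004 = 0.108.

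| Assumed net shift | Patients (237 × s) | Two-sided type I error |
|---|---|---|
| 0 | 0 | 5.0% |
| 0.5 points | 1.2 | 5.4% |
| 1 point | 2.4 | 6.5% |
| 2 points | 4.7 | 10.8% |
| 3 points | 7.1 | 17.8% |

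The shifts are assumptions. The documents give no basis for their size, or for any shift occurring.

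**The case against.** The strongest reply is that the protocol describes masking phase by phase, in terms of the treatment then being given. In the run-in the patient is masked to the run-in product; at month 6 everyone is known to be on active drug, and unmasked may mean no more than that. Section 5.5 has the randomisation system return kit numbers, the month 6 procedures list no code disclosure, and the only described way for a site to obtain an assignment is the safety route in Section 9.4. This reading is plausible, and disclosure of the randomised arm is not established. But the baseline entry in 3.1 uses the same construction for masking to the randomised arm, and nothing in 3.1 or 5.3 confines the month 6 sentence to the extension drug.

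A reader might also infer that the month 6 scores themselves are unmasked. They are not: unmasking starts only when the visit ends. Nor do the documents support the inference that PP membership will be decided by people who know the arm. Only patient and investigator are named, and the PP analysis is not the primary one.

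Source records must be contemporaneous and original (10.4.1), and the sponsor monitors sites (10.6). These controls narrow the route for biased correction but do not close it. Finally, the detailed analysis plan may contain masked-review rules. It is not part of the document reviewed, and it would not by itself change the instruction to sites in 3.1 and 5.3.

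**Conclusion.** The point holds as a gap in the masking rule. The text permits the randomised arm to reach sites before the primary lock for nearly all of about 474 planned month 6 completers. Entries that override responder status in the ITT analysis, and causality judgements, remain correctable in that interval. The count assumes that the 10% attrition is all before month 6.

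It is not shown that any arm will be disclosed, that anyone beyond patient and investigator is unmasked, or that bias will result. The size of any bias cannot be computed. The type I error figures show only that a net shift of a few patients would matter. The change is worth making because the safeguard is specific, nearly free and meets no stated competing need.

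**What to change.** In Sections 3.1 and 5.3, replace the unmasking sentence with a statement that treatment after month 6 is open label, but each patient's month 0–6 randomised assignment stays concealed from patient, site and study team until the primary database lock. Name two exceptions: safety unmasking under 9.4, and a firewalled release of codes for PK bioanalysis under 7.5. Without the second, the new sentence would conflict with 7.5.

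In Section 7.1, state that PP membership is fixed by masked staff before the primary (first) lock.

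The cost is a few sentences, a check that the randomisation system and extension supplies do not reveal the earlier arm, and a short description of the PK firewall. Sample size, visits and the treatment patients receive do not change.

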5.4 Treatment Allocation Ratio and Stratification

At the time of randomization (baseline, day 1), patients will be randomly assigned in a 1:1 ratio to receive either 0.1% AGN-195263 [REDACTED] or its vehicle

during the randomized study treatment phase. Patients will be stratified by gender and baseline (day 1) overall ocular discomfort score (1 vs 2 to 3). There will be 4 stratification groups as shown in Table 5.

Table 5 Stratification Groups

Stratification Group	Gender	Baseline Overall Ocular Discomfort Score
1	Male	1
2	Male	2 to 3
3	Female	1
4	Female	2 to 3

5.5 Method for Assignment to Treatment Groups/Randomization

Prior to initiation of screening procedures, each patient will provide informed consent. At the standardization (day -21) visit the site will call the interactive voice response system (IVRS) or log onto the interactive web response system (IWRS) to obtain the patient number that will serve as the patient identification number on all study documents.

An automated interactive (telephone or web) response system (IxRS) will be used to manage the run-in and randomization study treatment assignment based on randomization schemes prepared by Allergan Biostatistics. Study medication, including the run-in vehicle, will be labeled with medication kit numbers and shipped to each site.

At the time of enrollment at the vehicle run-in visit (day -14), all eligible patients will be assigned vehicle. At the patient's vehicle run-in visit, the IxRS system will provide the site with the specific medication kit number(s) to use for each qualified patient.

At the time of the baseline visit (randomization, day 1), patients meeting the inclusion/exclusion criteria ([Sections 4.3](#) and [4.4](#)) will be placed into 1 of 4 stratification groups as described in [Section 5.4](#). Eligible patients will be randomly assigned to receive either 0.1% AGN-195263 [REDACTED] or its vehicle in a 1:1 treatment allocation. Based on the randomization scheme, a randomization number associated with 1 of the 2 treatment arms will be assigned to each patient sequentially according to the order of enrollment within the patient's stratification group. That is, IxRS will assign the next available randomization number for the stratification group to the patient at the time the investigator requests randomization. IVRS/IWRS will report a medication kit number to use for each patient corresponding to the randomization number.

The site will dispense the study medication kit assigned by the IxRS according to the IVRS/IWRS instructions. Sites will also call the IVRS or log onto the IWRS at all subsequent visits to obtain a study medication kit number for dispensing study medication. Sites will receive the IxRS confirmation notifications for each transaction. All notifications are to be maintained with the study source documents.

5.6 Treatment Regimen and Dosing

All eligible patients will receive a 2-week (days -14 to -1) patient-masked run-in on vehicle instilled as a single drop twice daily in each eye. At baseline (randomization, [day 1]), upon meeting inclusion/exclusion criteria, patients will be randomized to 0.1% AGN-195263 or its vehicle to be administered as a single drop, twice daily (morning and evening) in each eye for 6 months (baseline [day 1] to month 6 visits). Starting at the month 6 visit, all patients will administer 0.1% AGN-195263 as a single drop, twice daily (morning and evening) in each eye for an additional 6 months (month 6 to month 12).

The patient or patient's caregiver may instill the SAT (during standardization period) and study treatment. Twice-daily (morning and evening) SAT (during standardization period) and study medication should be instilled approximately 12 hours apart each day at approximately the same times. Patients will be instructed to not administer their morning dose of SAT (prior to Vehicle Run-In (day -14) visit) or study treatment on the day of each study visit.

5.7 Storage of Study Medications/Treatments

The study treatment and SAT must be stored in a secure isolated area (ie, with no other medication, supplies, documents, etc) and administered only to patients entered into the clinical study, at no cost to the patient, in accordance with the conditions specified in this protocol. Since the active study treatment includes [REDACTED], the site and all principal/sub-investigators must have the appropriate national prescribing registration for handling controlled substances for the same location (ie, address) where patient visits take place or per applicable country regulations.

All study treatments must be stored in a secure, environmentally controlled, and monitored (manual or automated) area in accordance with the labeled storage conditions with access limited to the investigator and authorized site staff. Sites should monitor temperature conditions and report any temperature excursions to their site monitor or Allergan personnel. Please refer to the Procedure Manual for further details on drug storage and instructions on reporting temperature excursions. Study treatment and SAT are not to be frozen.

Allergan or Allergan designee will perform reconciliation on unused study treatment.

6. Response Measures and Summary of Data Collection Methods

[figure not shown]
6.1 Efficacy Measures

6.1.1 Primary Efficacy Measure

- Overall ocular discomfort score (0 to 4 scale; 0 = none, 4 = very severe)

6.1.2 Secondary Efficacy Measures

- TBUT (seconds)
- blurred vision score (0 to 4 scale; 0 = none, 4 = very severe)
- corneal sodium fluorescein staining (0 to 5 Oxford scheme)
- ocular burning score (0 to 4 scale; 0 = none, 4 = very severe)
- derived variables based on overall ocular discomfort score (change from baseline, ≥ 1 grade improvement from baseline, ≥ 2 grade improvement from baseline and $\geq 50\%$ improvement from baseline)

Term	Percentage
GMOs	95
Organic	95
Natural	95
Artificial	30
GMOs	95
Organic	95
Natural	95
Artificial	30
GMOs	95
Organic	95
Natural	95
Artificial	30
GMOs	95
Organic	95
Natural	95
Artificial	30

6.3 Safety Measures

- adverse events
- BCVA (LogMAR)
- biomicroscopy
- ophthalmoscopy
- intraocular pressure (IOP)
- urine pregnancy test (female patients only)
- PSA (male patients only)
- hematology, serum chemistry, and urinalysis
- vital signs
- male scalp hair evaluation assessed by the investigator using the Norwood Male Pattern Baldness grading scale
- female hair evaluation (upper lip, chin, cheeks, and scalp) assessed by the investigator using the Ferriman and Gallwey scoring (0 to 4) scale for facial hair and the Female Androgenetic Alopecia Ludwig grading scale for the scalp

6.5 Summary of Methods of Data Collection

This protocol will use electronic case report forms (eCRFs) with remote data capture through a qualified third-party vendor. Data entered into the eCRF will correspond to, and be supported by, source documentation maintained at the sites. The investigator is responsible for ensuring that data are properly recorded on each patient's eCRFs and related documents. The data will be entered on the eCRFs in a timely manner and on an ongoing basis. Site data and images will be transferred to Allergan via electronic media.

An IxRS will be used to assign patient identification numbers, randomize patients, and manage study medication inventory. Data will be transferred to Allergan on a periodic basis throughout the study.

7. Statistical Procedures

The primary efficacy analysis will be performed after all patients complete the month 6 visit or discontinue from the study prior to the month 6 visit. The final analysis will be performed after all patients exit the study. There will be separate database locks for the primary analysis and final analysis. Prior to the first database lock a detailed analysis plan (AP) will be approved.

7.1 Analysis Populations

There are 3 analysis populations defined for this study: intent-to-treat (ITT), per-protocol (PP), and safety.

The ITT population comprises all randomized patients. The efficacy variables will be analyzed using the ITT population. The analyses will be performed per the randomization schedule.

The PP population comprises all randomized and treated patients who met the key inclusion and exclusion criteria; did not use artificial tears (including SAT), lid hygiene, or other prohibited treatments that could impact the overall ocular discomfort score at month 6; and had no other major protocol deviations. The PP population will be determined prior to database lock. The primary efficacy variable will be analyzed using the PP population on an as-treated basis.

The safety population is defined as all patients who received at least 1 dose of study medication. Safety analyses will be performed on an as-treated basis. All safety measures will be analyzed using the safety population.

